The proportion of subjects who achieve HIV-1 RNA < 50 copies/mL at Weeks 96 and 144 and the proportion of subjects who achieve HIV-1 RNA < 20 copies/mL at Weeks 48, 96, and 144 as defined by the US FDA-defined snapshot algorithm will also be summarized. The 95% CIs will be constructed in the same manner as described for the primary efficacy endpoint.

The change from baseline in \log_{10} HIV-1 RNA and CD4+ cell count at Weeks 48, 96, and 144 will be summarized using descriptive statistics. The differences and the associated 2-sided 95% CIs will be constructed using an Analysis of Variance (ANOVA) model, including treatment (GS-9883/F/TAF vs. DTG + F/TAF), baseline HIV-1 RNA level ($\leq 100,000$ copies/mL vs. $> 100,000$ copies/mL), and region (US vs. Ex-US) as fixed effects in the model.

The proportion of subjects who achieve HIV-1 RNA < 50 copies/mL at Weeks 48 OL and 96 OL will be summarized, where missing HIV-1 RNA will be excluded and treated as failure, respectively. The changes from baseline in CD4+ cell count and percentage at Weeks 48 OL and 96 OL will be summarized using descriptive statistics.

Adverse events, clinical laboratory assessments, and pharmacokinetic parameters will be summarized using descriptive statistics.

A total of approximately 600 HIV-1 infected subjects, randomized in a 1:1 ratio to 2 treatment groups (300 subjects per treatment group), achieves at least 95% power to detect a non-inferiority margin of 12% in Week 48 response rate (HIV-1 RNA < 50 copies/mL as defined by the US FDA-defined snapshot algorithm) difference between the 2 treatment groups. For the sample size and power computation, it is assumed that both treatment groups have a response rate of 91% (based on Gilead Studies GS-US-292-0104 and GS-US-292-0111), that the non-inferiority margin is 12%, and that the significance level of the test is at a one-sided 0.025 level.

This study will be conducted in accordance with the guidelines of Good Clinical Practice (GCP) including archiving of essential documents.

GLOSSARY OF ABBREVIATIONS AND DEFINITION OF TERMS

° C	degrees Celsius
° F	degrees Fahrenheit
AE	adverse event
ALT	alanine aminotransferase
ANC	absolute neutrophil counts
ARV	antiretroviral
AST	aspartate aminotransferase
AUC	area under the plasma/serum/peripheral blood mononuclear cell concentration versus time curve
BID	twice a day
BUN	blood urea nitrogen
CBC	complete blood count
CI	confidence interval
CL _{cr}	creatinine clearance

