1.2.3.3. Summary of Phase 2 Study (GS-US-141-1475)

Study GS-US-141-1475 is an ongoing Phase 2, randomized, double-blind, multicenter, active-controlled study to assess the safety and efficacy of a regimen containing GS-9883+F/TAF versus dolutegravir (DTG)+F/TAF in HIV-infected, ART-naive adult subjects.

Eligible subjects were randomized in a 2:1 ratio to one of the following treatment groups, stratified by HIV-1 RNA level ($\leq 100,000$ copies/mL, $> 100,000$ copies/mL to $\leq 400,000$ copies/mL, or $> 400,000$ copies/mL) at screening:

- Treatment Group 1: GS-9883 75 mg + F/TAF (200/25 mg) + placebo-to-match DTG 50 mg once daily
- Treatment Group 2: DTG 50 mg + F/TAF (200/25 mg) + placebo-to-match GS-9883 75 mg once daily

Week 24 interim data are summarized below.

Subject Disposition and Baseline Characteristics

A total of 98 subjects were randomized and treated in the study: 65 subjects in the GS-9883+F/TAF group and 33 subjects in the DTG+F/TAF group. At the time of the Week 24 data analysis, 2 subjects (2.0%) had prematurely discontinued from the study, 1 in each treatment group; both subjects were lost to follow-up.

Demographic and baseline characteristics were similar between the 2 treatment groups.

Key baseline disease characteristics (ie, viral load, CD4 cell count, and eGFR_{CG}) were similar between the 2 treatment groups.

Median (first quartile [Q1], third quartile [Q3]) baseline HIV-1 RNA was 4.45 (3.96, 4.79) log₁₀ copies/mL, with 82.7% of subjects having $\leq 100,000$ copies/mL at baseline; 5 subjects had $> 400,000$ copies/mL at baseline; 4 of these subjects were randomized to GS-9883+F/TAF and 1 subject was randomized to DTG+F/TAF.

Median (Q1, Q3) baseline CD4 cell count was 444 (316, 595) cells/ μ L, with 41.8% of subjects having ≥ 500 cells/ μ L at baseline. Median (Q1, Q3) baseline eGFR_{CG} was 125.3 (105.7, 147.0) mL/min.

Efficacy Results

Virologic success at Weeks 12 and 24 was assessed using the US FDA-defined snapshot algorithm, defined as plasma HIV-1 RNA < 50 copies/mL. At Weeks 12 and 24, virologic success was high and similar between the 2 treatment groups as follows: Week 12 GS-9883+F/TAF 93.8%, DTG+F/TAF 93.9% (stratum-adjusted difference in percentages: -1.3% ; 95% CI: -12.9% to 10.2% ; $p = 0.79$); Week 24 GS-9883+F/TAF 95.4%, DTG+F/TAF 93.9% (1.0%; 95% CI: -10.7% to 12.7% ; $p = 0.84$).

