Of the 5 subjects with baseline viral load $> 400,000$ copies/mL, 4 had HIV-1 RNA < 50 copies/mL at Week 24, and 1 had HIV-1 RNA of 60 copies/mL.

Following initiation of study drug, the increases from baseline in CD4 cell count were similar between treatment groups. Mean (SD) baseline CD4 cell counts were as follows: GS-9883+F/TAF 471 (190.9) cells/ μ L; DTG+F/TAF 507 (271.0) cells/ μ L; $p = 0.35$. The mean (SD) change in CD4 cell count from baseline to Week 12 was similar between the 2 treatment groups as follows: GS-9883+F/TAF, +170 (150.0) cells/ μ L; DTG+F/TAF, +173 (220.5) cells/ μ L (difference in least squares mean [LSM]: 0; 95% CI: -76 to 76; $p = 1.00$). There were similar increases in the mean (SD) CD4 cell count in both treatment groups Week 24: GS-9883+F/TAF, +189 (177.8) cells/ μ L; DTG+F/TAF, +157 (163.2) cells/ μ L (difference in LSM: 39; 95% CI: -35 to 113; $p = 0.30$).

Interim Virology Resistance Data

Through Week 24, no emergent drug resistance was detected.

Safety Results

Adverse Events

The overall incidence of treatment-emergent AEs was balanced between treatment groups as follows: GS-9883+F/TAF 66.2%, 43 subjects; DTG+F/TAF 57.6%, 19 subjects. The most common treatment-emergent AEs (occurring in > 2 subjects) by treatment group were as follows:

- **GS-9883+F/TAF:** diarrhea and headache (7.7%, 5 subjects each); and nausea, decreased appetite, arthralgia, and cough (4.6%, 3 subjects each)
- **DTG+F/TAF:** nausea (12.1%, 4 subjects); diarrhea (9.1%, 3 subjects)

Most treatment-emergent AEs were Grade 1 in severity. Grade 3 or 4 AEs were reported in only 1 subject (Grade 3 diabetic ketoacidosis), in the GS-9883+F/TAF group; this event was also reported as an SAE. One other SAE (appendicitis), also in the GS-9883+F/TAF group, was reported. Neither SAE was considered related to study drug by the investigator or resulted in study drug discontinuation or interruption, and both SAEs resolved.

The overall incidence of study drug-related treatment-emergent AEs was balanced between treatment groups as follows: GS-9883+F/TAF 15.4%, 10 subjects; DTG+F/TAF 18.2%, 6 subjects. Most study drug-related treatment-emergent AEs were Grade 1 in severity. Grade 2 study drug-related treatment-emergent AEs were reported in 1 subject in the GS-9883+F/TAF group (somnolence and headache) and 1 subject in the DTG+F/TAF group (vomiting). There were no Grade 3 or 4 treatment-emergent AEs or SAEs reported that were considered related to study drug.

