6.2.2. Day 1 Assessments

The following evaluations are to be completed at the Day 1 Visit. **The Investigator must have received the results from the screening genotype report and confirmed eligibility before proceeding with the Day 1 visit.** The subject must complete all study procedures before being administered the study drug:

- Review of AEs and changes in concomitant medications
- Complete physical examination (urogenital/anorectal exams will be performed at the discretion of the Investigator)
- Vital signs measurement (blood pressure, pulse, respiration rate, and temperature), including weight
- 12-lead ECG performed supine
- Short Form 36 Health Survey (SF-36), HIV Symptoms Distress Module, Work Productivity and Activity Impairment Questionnaire (WPAI) and Pittsburgh Sleep Quality Index (PSQI) to be completed by the subject. Subject is to read questionnaire by himself/herself and write/mark answers directly onto questionnaires.
- Urine collection for the following laboratory procedures:
 - Urinalysis
 - Urine pregnancy test (females of childbearing potential only); positive urine pregnancy tests will be confirmed with a serum test. If the test is positive, the subject will not be able to participate

CC

- Blood sample collection for the following laboratory analyses:
 - Chemistry profile: alkaline phosphatase, AST, ALT, GGT, total bilirubin, direct and indirect bilirubin, total protein, albumin, LDH, CPK, bicarbonate, BUN, calcium, chloride, creatinine, phosphorus, magnesium, potassium, sodium, uric acid, amylase (reflex lipase testing is performed in subjects with total amylase > 1.5 × ULN) and TSH. PT/INR (prothrombin time/international normalized ratio)
 - Metabolic assessments: Fasting (no food or drinks, except water, at least 8 hours prior to blood collection) glucose and lipid panel (total cholesterol, HDL, direct LDL, and triglycerides). If the subject has not fasted prior to the visit, the visit may proceed, but the subject must return within 72 hours in a fasted state to draw blood for the metabolic assessments.
 - Estimated glomerular filtration rate according to the Cockcroft-Gault formula
 - Hematology profile: complete blood count (CBC) with differential and platelet count
 - Plasma HIV-1 RNA
 - CD4+ cell count
 - Plasma storage sample for safety, virology, or PK testing

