6.4. Treatment Assessments (Week 4 -144)

The following evaluations are to be completed at the end of Weeks 4, 8, 12, 24, 36, 48, 60, 72, 84, 96, 108, 120, 132, and 144 unless otherwise specified.

Study visits are to be completed within ± 2 days of the protocol-specified visit date based on the Day 1 visit through Week 12 and completed within ± 6 days of the protocol-specified visit date through Week 144, unless otherwise specified. The visit window at Weeks 48, 96 and 144 will be ± 6 weeks of the protocol-specified visit date, and these clinical visit windows coincide with the Weeks 48, 96 and 144 statistical analysis window for HIV-1 RNA.

Regularly scheduled evaluations will be made on all subjects whether or not they continue to receive study drug.

- Review of AEs and changes in concomitant medications
- Complete physical examination (**Weeks 24, 48, 96, 144**) (urogenital/anorectal exams will be performed at the discretion of the Investigator) or symptom-directed physical examination as needed
- Vital signs measurement (blood pressure, pulse, respiration rate, and temperature), including weight
- 12-lead ECG performed supine (**Weeks 24, 48, 96, 144**)
- Short Form 36 Health Survey (SF-36), HIV Symptoms Distress Module, Work Productivity and Activity Impairment Questionnaire (WPAI) and Pittsburgh Sleep Quality Index (PSQI) to be completed by the subject at **Weeks 4, 12 and 48**. Subject is to read questionnaire by himself/herself and write/mark answers directly onto questionnaires.

- Urine collection for the following laboratory procedures:
 - Urinalysis
 - Urine pregnancy test (females of childbearing potential only); positive urine pregnancy tests will be confirmed with a serum test. If the test is positive, the subject will be discontinued
- CCI
- Blood sample collection for the following laboratory analyses:
 - Chemistry profile: alkaline phosphatase, AST, ALT, GGT, total bilirubin, direct and indirect bilirubin, total protein, albumin, LDH, CPK, bicarbonate, BUN, calcium, chloride, creatinine, glucose, phosphorus, magnesium, potassium, sodium, uric acid, and amylase (reflex lipase testing is performed in subjects with total amylase $> 1.5 \times$ ULN). At Weeks 12, 24, 48, 72, 96, 120, and 144 analyses of glucose will be done as part of the fasting metabolic assessments and not as part of the chemistry profile. At Weeks 24, 48, 72, 96, 120 and 144, TSH will also be analyzed.

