8.3. Data Handling Conventions

HIV-1 RNA results of “No HIV-1 RNA detected” and “<20 cp/mL HIV-1 RNA Detected” will be imputed as 19 copies/mL for analysis purpose. Logarithm (base 10) transformation will be applied to HIV-1 RNA levels for efficacy analysis.

Natural logarithmic transformation of plasma concentrations and PK parameters will be applied for PK analysis.

Laboratory data that are continuous in nature but are less than the lower limit of quantitation or above the upper limit of quantitation will be imputed to the value of the lower or upper limit plus or minus one significant digit, respectively (eg, if the result of a continuous laboratory test is < 20, a value of 19 will be assigned).

Missing data can have an impact upon the interpretation of the trial data. In general, values for missing data will not be imputed. However, a missing pre-treatment laboratory result would be treated as normal (ie, no toxicity grade) for the laboratory abnormality summary.

All available data for subjects that do not complete the study will be included in data listings.

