8.5.2. Secondary Analyses

The proportion of subjects who achieve HIV-1 RNA < 50 copies/mL at Weeks 96 and 144 and the proportion of subjects who achieve HIV-1 RNA < 20 copies/mL at Weeks 48, 96 and 144, as defined by the US FDA-defined snapshot algorithm, will be analyzed using the same method as for the primary efficacy endpoint.

The changes from baseline in log₁₀ HIV-1 RNA and CD4+ cell count at Weeks 48, 96, and 144 will be summarized by treatment using descriptive statistics. The differences in changes from baseline in log₁₀ HIV-1 RNA and CD4+ cell count between 2 treatments groups and the associated 95% confidence intervals will be constructed using ANOVA models, including treatment (GS-9883/F/TAF vs. DTG + F/TAF), baseline HIV-1 RNA level ($\leq 100,000$ copies/mL vs. $> 100,000$ copies/mL), and region (US vs. Ex-US) as fixed effects in the model.

In addition, missing CD4+ cell count will be imputed using Last Observation Carried Forward (LOCF) method and analyzed similarly.

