8.9. Sample Size

A total of approximately 600 HIV-1 infected subjects, randomized in a 1:1 ratio to 2 treatment groups (300 subjects per treatment group), achieves at least 95% power to detect a non-inferiority margin of 12% in Week 48 response rate (HIV-1 RNA < 50 copies/mL as defined by the US FDA-defined snapshot algorithm) difference between the 2 treatment groups. For the sample size and power computations, it is assumed that both treatment groups have a response rate of 91% (based on Gilead Studies GS-US-292-0104 and GS-US-292-0111), that the non-inferiority margin is 12%, and that the significance level of the test is at a one-sided 0.025 level. Sample size and power calculations were made using the statistical software package nQuery Advisor (Version 6.0).

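### Adjusting change in log10 HIV-1 RNA for baseline only as a two-level category gives a valid but needlessly wide confidence interval

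*Protocol*

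**What the plan says.** Protocol 8.5.2 compares the arms on change from baseline in log10 HIV-1 RNA and in CD4+ count at Weeks 48, 96 and 144. The differences and 95% CIs are "constructed using ANOVA models, including treatment (GS-9883/F/TAF vs. DTG + F/TAF), baseline HIV-1 RNA level" in two categories (at or below versus above 100,000 copies/mL), and region. The synopsis says the same: "The differences and the associated 2-sided 95% CIs will be constructed using an Analysis of Variance (ANOVA) model", with the same three terms. No continuous baseline RNA appears, and baseline CD4 does not enter in any form.

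Three other places bear on the point:

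- Protocol 8.3: RNA results below 20 copies/mL "will be imputed as 19 copies/mL for analysis purpose", and RNA is analysed on the log10 scale.
- Protocol 8.9: for the sample size, "it is assumed that both treatment groups have a response rate of 91" percent at Week 48.
- Protocol 6.2.2: the Day 1 blood draw includes "Plasma HIV-1 RNA" and a CD4+ count, so both baseline values exist.

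SAP Section 6 states that the Week 48, 96 and 144 secondary analyses have been performed and will not be repeated. SAP 6.2.1 refers to earlier interim SAPs for their methods. SAP 6.4 plans no change from the protocol's efficacy analysis.

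**The concern.** A change score carries all the between-subject spread of the baseline unless the model removes it. For RNA this matters more than usual, because the Week 48 value barely varies in most subjects: anything below 50 copies/mL lies between log10(19) = 1.28 and log10(50) = 1.70. Change is then nearly a fixed number minus baseline. A single cut with most subjects on one side explains less than half of the baseline spread, and the rest goes into the residual variance and widens the interval.

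At stake is the precision of two named secondary comparisons at three time points. No margin, power claim or multiplicity control attaches to them.

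**Working it through.** **The plan's own figure.** The only power stated is at least 95% for the primary test. With 91% in both arms, a 12% margin, 300 per arm and one-sided 0.025, SE = sqrt(2 × 0.91 × 0.09/300) = 0.0234. Power is Φ(0.12/0.0234 − 1.96) = 99.9%, so the claim is met. No SD, width or power is stated for the continuous endpoints.

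**Baseline variance left by the split.** The Phase 2 summary (Protocol 1.2.3.3) gives quartiles of 3.96 and 4.79 log10, with 82.7% of subjects at or below 100,000 copies/mL. Assuming normality:

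- SD = (4.79 − 3.96)/(2 × 0.6745) = 0.615
- Cut point z = 0.942, so mean = 5 − 0.942 × 0.615 = 4.42
- Share of variance removed = φ(0.942)²/(0.827 × 0.173) = 0.458
- Within-category SD = 0.615 × sqrt(0.542) = 0.453 (variance 0.205)

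So 54% of the baseline variance stays in the residual.

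**Width of the RNA interval.** Assumptions: 300 analysed per arm; a share p of Week 48 values at or above 50 copies/mL; 85% of the rest at 19 copies/mL and 15% spread evenly on the log scale from 20 to 50; Week 48 value Y independent of baseline. Values at or above 50 follow, on the log10 scale, N(2.0, 0.3), N(2.5, 0.5), N(3.0, 0.7) or N(4.0, 0.7) (mean, SD), cut below at log10(50).

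Half-width = 1.96 × sqrt(2 × V/300), with V = 0.205 + var(Y) for the planned ANOVA and V = var(Y) with continuous baseline added.

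Example, p = 3% and N(3.0, 0.7): var(Y) = 0.109. ANOVA: 1.96 × sqrt(2 × 0.314/300) = 0.090. ANCOVA: 1.96 × sqrt(2 × 0.109/300) = 0.053. Ratio 1.70.

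| Share ≥ 50 copies/mL | ANOVA half-width (log10) | ANCOVA half-width (log10) | Ratio, lowest to highest tail |
|---|---|---|---|
| 1% | 0.075–0.086 | 0.019–0.047 | 3.88 to 1.85 |
| 3% | 0.077–0.106 | 0.026–0.077 | 2.93 to 1.37 |
| 5% | 0.079–0.122 | 0.032–0.098 | 2.50 to 1.24 |
| 9% | 0.083–0.147 | 0.040–0.128 | 2.08 to 1.15 |

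With 80% to 90% at the floor, the extremes are 1.15 and 4.2. The low end applies when values at or above 50 are mostly high. That could happen if off-drug values are analysed, since under Protocol 6.4 "Regularly scheduled evaluations will be made on all subjects whether or not they continue to receive study drug".

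**Separate simulation.** This used 270 analysed per arm, baseline truncated at the 500 copies/mL entry limit, a different tail, and 1,500 trials per scenario. At baseline SD 0.615 the half-width fell from 0.080 to 0.027 (0.5% at or above 50), 0.091 to 0.053 (2%), 0.110 to 0.082 (5%) and 0.130 to 0.107 (9%). Across baseline SDs of 0.50 to 0.75 the interval was 14% to 69% narrower. With no treatment effect, coverage was 94% to 96% for the ANOVA and 94% to 97% with the covariate. The extra degree of freedom widens the interval by about 0.1%.

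**CD4.** Pooled Phase 2 Week 24 change SD, from 177.8 (n = 65) and 163.2 (n = 33), is 173, so the half-width is 1.96 × 173 × sqrt(2/300) = 27.7 cells/µL. Adding baseline CD4 narrows this by 1 − sqrt(1 − r²): 0.5% at r = 0.1, 4.6% at 0.3, 13.4% at 0.5 in absolute value (correlations assumed). Pooled baseline SD, from 190.9 and 271.0, is 221, so a one-SE chance gap is 221 × sqrt(2/300) = 18 cells. Such a gap shifts the unadjusted estimate by r × 173 × sqrt(2/300), or 1.4 to 7 cells, and by less under randomisation stratified on screening CD4.

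**The case against.** The strongest reply is that nothing is wrong. The ANOVA is unbiased with nominal coverage, and a preference for a more efficient model is optional on endpoints with no margin or power claim. The planned RNA half-widths, 0.075 to 0.147 log10, are already only about 2% to 5% of an expected fall near 3.2 log10 (4.45 − 1.28). After adjustment the contrast rests on a few viraemic subjects, whom the < 50 and < 20 copies/mL endpoints already describe. All of this stands as a limit on importance.

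The size of the gain is not fixed by the documents. The tail, the floor share and the number analysed are assumed, and the formula treats Week 48 RNA as independent of baseline. Making viraemia three times as frequent above 100,000 copies/mL cut the gain from 42% to 36% (2% base share, 300 per arm). The 9% row is also high, because snapshot non-response includes subjects with no data. These points change the size but not the direction.

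ANCOVA is not flawless. With 0.1% viraemic in one arm, 1% in the other and a high tail, simulated coverage was about 91% to 92%, against 95.2% for the ANOVA. This is an extreme rare-event imbalance; at larger shares both models were close to 95%. It is a reason to keep the ANOVA alongside.

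Finally, the analyses are complete and the interim SAPs were not available. A post hoc model carries less weight, and a baseline-adjusted analysis may already exist. The recommendation allows for both.

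**Conclusion.** The concern holds as a point of efficiency. The planned model leaves about 54% of baseline RNA variance in the residual, and its interval is about 1.15 to 3.9 times as wide as one adjusted for continuous baseline log10 RNA. The direction held in every scenario tried. The size rests on the Phase 2 baseline spread and an assumed distribution of Week 48 values at or above 50 copies/mL. For CD4 the gain is small and depends on an unreported correlation. The planned intervals remain valid, and the primary endpoint, its strata and its power are untouched. This is a worthwhile improvement to make; it is not a defect that undermines a result.

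**What to change.** Fit an ANCOVA that keeps treatment, baseline RNA category and region. Add continuous baseline log10 HIV-1 RNA to the RNA-change model and baseline CD4+ count to the CD4-change model. RNA is the priority; CD4 is for completeness. Report the results at Weeks 48, 96 and 144 as supplementary, labelled post hoc, beside the planned ANOVA and not in its place. If an interim SAP already specifies a baseline-adjusted analysis, cite that instead. Leave the primary Mantel-Haenszel strata as they are.

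The cost is one model term (one degree of freedom) per outcome, no new data, and one supplementary output covering three time points.

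### CD4 change is planned as an observed-case ANOVA plus an added LOCF run; each can bias the gain, in opposite directions, and a repeated-measures model with baseline CD4 should be the main analysis

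*Protocol*

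**What the plan says.** CD4 change from baseline at Weeks 48, 96 and 144 is a named secondary endpoint (Protocol Sections 3.1 and 8.1.3). Section 8.5.2 first specifies an ANOVA at those weeks with treatment, baseline HIV-1 RNA stratum and region as fixed effects, giving an arm difference and a 95% CI. It states no imputation for that analysis. Section 8.3 sets the default, "In general, values for missing data will not be imputed", so the first-listed ANOVA is read here as observed-case.

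LOCF comes second, as an addition: "missing CD4+ cell count will be imputed using Last Observation Carried Forward (LOCF) method and analyzed similarly", with the filled values put through the same kind of model. The synopsis does not mention it. No reason or missing-data assumption is given for either analysis.

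CD4 is collected at Weeks 4, 8 and 12 and then every 12 weeks, and scheduled evaluations continue after a subject stops study drug (Section 6.4, Appendix 2). Section 8.5.2 does not say whether CD4 values after stopping drug count.

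The supplied SAP covers the final analysis. Its Section 6.3.2.2 summarises CD4 descriptively, on treatment only, without LOCF. Sections 6 and 6.2.1 refer the Week 48, 96 and 144 analyses to earlier SAPs or programming specifications, which are not among the documents, and say that those analyses will not be repeated.

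**The concern.** Carrying a value forward treats a subject's CD4 as fixed from the last visit. A Week 12 count can stand in for Week 48, or for Week 144, 132 weeks later. If CD4 is still rising on treatment, the carried value is too low on average, even when dropout has nothing to do with CD4.

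The observed-case ANOVA has a different weakness. It drops every earlier visit of a subject with no value at the analysis week, so if subjects with poor CD4 response leave more often, those who remain overstate the gain. The plan therefore pairs two analyses that can err in opposite directions and has no rule for which to believe if they disagree.

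Neither analysis adjusts for baseline CD4, although screening CD4 was a randomization stratum. Section 8.5.1.3 leaves CD4 out of the primary analysis because of sparse strata and its correlation with HIV-1 RNA. The sparse-strata reason does not apply to a continuous covariate in a linear model.

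At stake are the reported CD4 gain in each arm and, if dropout differs, the arm difference.

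**Working it through.** **Figures in the plan.** The documents give no SE, power or bias figure for CD4. The only power statement is for the primary endpoint, and it reproduces: SE = √(2 × 0.91 × 0.09 / 300) = 0.0234; 0.12/0.0234 - 1.96 = 3.17; power 99.9%, consistent with at least 95%.

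**Inputs from the documents.** 300 per arm (Section 8.9). Phase 2 CD4 change (Section 1.2.3.3): Week 12 "GS-9883+F/TAF, +170 (150.0) cells" and "DTG+F/TAF, +173 (220.5) cells"; Week 24 "GS-9883+F/TAF, +189 (177.8) cells" and, for DTG, +157 (SD 163.2). Weighted by 65 and 33 subjects:
- Week 12: (65 × 170 + 33 × 173)/98 = 171
- Week 24: (65 × 189 + 33 × 157)/98 = 178
- Pooled Week 24 SD: √[(64 × 177.8² + 32 × 163.2²)/96] = 173.1

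**Assumed inputs.** Share missing at Week 48: 9%, 15%, or 12% versus 6%. The 9% is everything outside the planned 91% response, so it is a planning ceiling for a missing Week 48 visit. Phase 2 discontinuation by Week 24 was 2 of 98, one per arm. Also assumed are the Week 48 gain (+200 or +230 cells), the correlation between visits, and the dropout mechanism (random, or lower CD4 more likely to leave).

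**Closed form for LOCF.** With d the share missing and g the gap between the final mean and the carried mean, within-arm bias = -d × g:
- 2% × 50 = -1.0
- 9% × 50 = -4.5
- 15% × 100 = -15

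With equal trajectories, bias in the difference = -(d1 - d2) × g: zero for equal dropout, and 3 points × 50 = -1.5.

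**Simulation to Week 48.** 300 per arm, 2,500 runs per row, no true arm difference. Each cell shows within-arm bias / bias in the difference, in cells/µL. In unequal rows the within-arm figure is for the 12% arm, and the difference is that arm minus the other. Repeated measures is the likelihood estimate for monotone normal data.

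| Missing | Who leaves | Gain | Observed-case | LOCF | Repeated measures |
|---|---|---|---|---|---|
| 9/9% | random | 200 | -0.2 / -0.13 | -4.6 / -0.15 | -0.1 / -0.13 |
| 9/9% | random | 230 | -0.3 / -0.47 | -7.1 / -0.27 | -0.3 / -0.38 |
| 9/9% | low CD4 | 200 | +7.2 / -0.29 | -7.5 / -0.18 | 0.0 / -0.24 |
| 9/9% | low CD4 | 230 | +7.2 / -0.30 | -9.8 / -0.07 | +0.1 / -0.21 |
| 15/15% | random | 200 | +0.2 / -0.02 | -7.3 / +0.05 | +0.1 / -0.06 |
| 15/15% | random | 230 | +0.5 / +0.15 | -11.1 / +0.25 | +0.5 / +0.21 |
| 15/15% | low CD4 | 200 | +11.8 / -0.54 | -13.0 / -0.52 | -0.5 / -0.48 |
| 15/15% | low CD4 | 230 | +12.4 / -0.09 | -16.3 / +0.09 | +0.2 / +0.01 |
| 12/6% | random | 200 | +0.4 / +0.62 | -5.5 / -2.51 | +0.5 / +0.60 |
| 12/6% | random | 230 | +0.5 / +0.51 | -8.8 / -4.14 | +0.4 / +0.53 |
| 12/6% | low CD4 | 200 | +9.5 / +5.16 | -10.3 / -4.95 | -0.3 / +0.12 |
| 12/6% | low CD4 | 230 | +9.9 / +5.20 | -12.9 / -6.25 | +0.2 / +0.25 |

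Simulation error in a difference is about 15.8/√2500 = 0.3. One further run, with a true difference of 30 cells, 9% missing in each arm and low CD4 leaving, gave an LOCF bias of -11.2 in the better arm and -1.4 in the difference.

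**Scale.** Complete data give a half-width of 1.96 × 173.1 × √(2/300) = 27.7. LOCF model SEs of 14.97 to 15.75 give 29.3 to 30.9. The largest LOCF shift is 6.25/15.51 = 0.40 of an SE.

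**Standard error of LOCF.** The mean model SE against the actual sampling SD of the LOCF estimate is 15.01 vs 14.89 (9%, random, +200) and 14.97 vs 14.90 (15%, random, +200). Coverage over all rows is 93.3% to 95.6%. Against the sampling SD of the repeated-measures estimate under random, equal dropout, the LOCF SE is smaller by 2 to 4% at 9% (15.01/15.39 = 0.975; 15.10/15.75 = 0.959) and by 5 to 7% at 15% (14.97/15.83 = 0.946; 15.08/16.26 = 0.927).

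**The case against.** The strongest reply is that LOCF is only an addition to an observed-data analysis of a secondary endpoint. It carries no alpha adjustment (SAP Section 3.5) and does not touch the Week 48 snapshot result. That is correct and limits the importance of the point. It does not remove it, because the companion ANOVA is itself biased when low-CD4 subjects leave.

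Two stronger readings are tempting, and the documents do not support them.
- A reader might infer that LOCF understates its standard error because filled values count as data. In the simulation the LOCF SE tracks the estimate's own sampling error and coverage stays near 95%. The SE is only modestly smaller than that of a likelihood estimate.
- A reader might infer from Phase 2 that carried values err differently by arm, since the means moved by +19 and -16 between Weeks 12 and 24. Those arms had 65 and 33 subjects. The DTG means alone have SEs of 220.5/√33 = 38 and 163.2/√33 = 28, and the reported arm differences are 0 (95% CI -76 to 76) and 39 (-35 to 113). These shifts are compatible with noise. Phase 2 also stops at Week 24, so it cannot show how fast CD4 rises later.

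It also stands that the earlier SAPs may have dropped LOCF or specified missing CD4 differently. That cannot be checked here.

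**Conclusion.** The point holds as a modest one about a secondary endpoint. If CD4 is still rising, LOCF lowers the Week 48 within-arm gain by about 5 to 10 cells at an assumed 9% missing. The observed-case ANOVA raises it by about 7 cells at 9% if low-CD4 subjects leave, and is essentially unbiased if dropout is random. For the arm difference, both are near zero with equal dropout and equal trajectories. At an assumed 12% versus 6%, LOCF moves the difference by -2.5 to -6.3 cells, and observed-case by about +5 under low-CD4 dropout. That is small beside a half-width near 30. The repeated-measures estimate stayed within about 0.5 cells within arm and 0.6 in the difference in every row of the table, but those scenarios all satisfy its missing-at-random assumption.

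The sizes rest on assumed dropout, Week 48 gain, correlation and mechanism, none of which the documents give. Weeks 96 and 144 were not simulated. The primary endpoint is unaffected.

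**What to change.** In Protocol Section 8.5.2, make the main CD4 analysis a mixed model for repeated measures on all scheduled CD4 values. Include treatment, visit, treatment-by-visit, baseline CD4, baseline HIV-1 RNA stratum and region, with unstructured covariance, and report the Week 48, 96 and 144 contrasts. State the missing-at-random assumption, and state whether values after stopping study drug are included, since visits continue off drug and the choice changes what is estimated. Keep LOCF at most as a labelled sensitivity analysis. Removing LOCF alone would not be enough, because the observed-case ANOVA would remain the main analysis.

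The cost is a paragraph of text and one standard procedure, with no new data. With 14 post-baseline visits to Week 144 the unstructured matrix has 14 × 15/2 = 105 parameters, so name a fallback structure in case it does not converge. The method relies on missing at random, which the data cannot verify. Because the Week 48 to 144 analyses were completed under earlier SAPs, applying it now would be a supplementary reanalysis and should be reported as such.
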